Some programs do the screening, refraction testing and provision of spectacles to children entirely in the school setting ("School Model"). One strength of such programs are that most children at school who need spectacles get them. However, sustainability is poor, because spectacles cannot be sold in many schools and there may be too few refractionists to cover all schools in most countries. Other programs provide vision screening at schools, but refer children who fail vision screening to nearby facilities for refraction and distribution/sale of spectacles ("Referral Model"). This model's strengths include lower demand on refractionists and opportunities for the spectacles to be sold. However, a disadvantage is that most of the referred children do not attend the specialist facility. One way to improve this might be to enhance the Referral Model and a recent USAID review by [name] and [name] showed that involving teachers in vision screening and family counseling significantly increases children's use of spectacles. Therefore, at 141 schools in India, involving over 42,300 children (assuming a minimum of 300 children/school), the investigators will study an "Improved Referral Model," with strong teacher involvement, to investigate the potential benefits of combining the lower costs of the "Referral Model" with the high uptake of the "School Model". The investigators will also assess the effects of allowing parents to purchase enhanced spectacles, rather than having their child use the free spectacles. Children will be randomized by school to the "School Model," "(Improved) Referral Model" or the "(Improved) Referral Model + Cost Recovery (sale of "upgrade spectacles" alongside offering free spectacles. The main study outcome will be program cost-effectiveness, defined as the program cost per child identified with correctable refractive error, who receives spectacles, and wears them at an un-announced visit 3 month after distribution. Profit on spectacles sold in the "Referral + Cost Recovery" group will be subtracted from the program costs in this study group. The groups will be compared, with and without adjustment for baseline characteristics.

Detailed Description:

Background

Need: The leading cause of vision impairment among children in India, and in the world more widely, is an uncorrected refractive error (URE). For example, the population-based Refractive Error Studies in Children (RESC) studies found that 61% of vision impairment in rural children[1] and 89% in urban children[2] in India was due to URE, and that as few as 10% of rural and 35% of urban children who need spectacles actually had them.[1,2,3] The impact of this shortfall in service delivery is highlighted by recent randomized trials in Asia showing that provision of spectacles significantly improves children's educational outcomes,[4] and the shortcoming in India is particularly important because India has the highest number children of any other country.[5]

Potential impact: This trial has the potential to impact on at least two of the Sustainable Development Goals (SDG) of the United Nations. Although interventions to prevent myopia, such as topical anti-muscarinic therapy[6] and increased time outdoors[7], show much promise, they are not yet ready for large-scale use. Until then, school vision programs remain the principle tool to address the problem of URE in India and elsewhere, and thereby improving children's access to high-quality education (SDG #4) and helping to address unequal access of girls to healthcare services affecting vision (SDG #5).[8] In fact, the Indian government and many private entities are already taking a very active role in school vision screening. Since the onset of the Sarva Shiksha Abhiyan (Education for All)

program in 2002, many millions of children have undergone school vision screening, but refraction and spectacles distribution has been limited and much more could be done to help. To sustain and expand these efforts, more cost-effective approaches are needed.

Problems with current models: Many non-governmental organization (NGO) and government spectacle distribution programs in India and elsewhere use school-based vision screening, refraction and provision of spectacles. This is particularly true in poorer, rural or other under-served areas. The greatest strength of such programs is that they deliver refractive services and spectacles to a large proportion of children requiring them when school attendance rates are high. However, sustainability is problematic: these programs usually deliver spectacles for free, because their sale is not permitted in many schools. Further, this model is very demanding on resources, because refractionists must travel to numerous schools in their catchment area. Finally, it has been suggested that long-term compliance with spectacle wear may be higher when families make at least some contribution to spectacle costs, although evidence for this assertion is lacking.[9]

Alternatively, other programs, particularly those in urban or better-served areas, may provide vision screening at schools, but then refer children and families failing to screen to a nearby facility for refraction and distribution or sale of spectacles. The strength of this model is that it is less demanding of resources (refractionists remain at their base facility rather than being directly involved in outreach screening) and spectacle sales at medical facilities are often more acceptable than sales in schools. Therefore, this model may be more sustainable. However, program experience and research [10] have shown up to two-third of the referred children/families do not attend the facility that they are referred to.

Potential superiority of optimized Referral Models and improvements for vulnerable children: Recent evidence from a review by [name] and [name][11,12] and trials by [name][13] suggest that various strategies which increase involvement of teachers in the screening process (parent-teacher meetings; short message service (SMS), phone call, or handwritten notes in the students diary from teachers to families who do not complete referrals) can significantly increase the proportion of families following up for care at an outside eye care facility. Therefore, this cluster randomized trial will test an "optimized" model of distribution of spectacles, maximizing teacher involvement, to determine whether this approach can achieve comparable service uptake to fully school-based models at a greater level of cost-effectiveness. High-quality, trial-based evidence that showed that optimized Referral models are both low-cost and high-coverage may provide a strong stimulus to scale up refractive service programs in India and other low-middle income countries (LMICs). These programs can benefit millions of low-income children not currently receiving refractive services, thus improving their access to classroom learning.

This trial will compare two general screening methods: 1. School model and 2. Referral Model. A "Cost model", which is builds on the Referral model but includes the sale of spectacles, will also be included, as a third randomized group. In the School model, refraction occurs at the school and spectacles are given to children at the school, which may yield a higher rate of compliance, but is more expensive and may not be sustainable. On the other hand, the Referral model, where the children are referred to be screened at the vision center or service center may have lower compliance but be less expensive and more likely to be sustainable. This study examines the hypothesis that greater teacher involvement in screening and follow up can improve the compliance of children and families with the examination at the service center in the Referral model. For this reason, the main outcome of the trial is cost-effectiveness (amount spent per child who receives spectacles that improve his/her vision, and which are worn at an un-announced examination three months after distribution). If the teacher intervention can improve compliance in the Referral model,

it will most likely be the more cost-effective model. If the teacher's intervention doesn't increase compliance in the Referral model, then the School model is likely to be the most cost-effective. Because money invested in school screening is wasted when families do not comply with referral to the Vision Centre in the Referral model, compliance with a referral will be the most important determinant of our main cost-effectiveness outcome.

Experimental plan Population: School children in the 6th to 10th grades (11-15 years of age) at public and private, rural and urban schools with a minimum of 300 students and covered by the Orbis India REACH (Refractive Error Among Children) program, including those located nearer and further from Vision Centers, which will serve as the principle eye care facilities in the study.

Eligibility: Enrolment criteria: Children in randomly-selected 6th to 10th grades in selected schools with presenting visual acuity (that is, wearing spectacles if spectacles are owned at baseline) \leq 6/9.6 (0.2 LogMAR) in either eye. Children who already own spectacles will be requested to bring their spectacles on the day of screening, and children whose vision with existing spectacles meets study criteria will be eligible. Exclusion criteria: Parents returning the form indicating they do not wish their child to participate; no Vision Center within 50 km of the child's home (a rare occurrence in the REACH network). If the child is incapable of completing visual acuity screening in both eyes for any reason.

Sample size: At a refractive error prevalence of 3%, with minimum of 300 children/school, 95% of children receiving spectacles in the School Model, 40% of children wearing them in both the School Model and Referral Model groups at un-announced 3 month visits, a cost of US\$1.30 per child screened in the School Model and US\$0.80 in the Referral Model (all assumptions based on REACH Program data), if 58.5% of families accept referral to receive refraction and spectacles in the Referral Model, this would reach the same cost-effectiveness as the School Model. A total of 141 schools (47 in each of three groups) across three participating hospitals would be sufficient to detect significantly better cost-effectiveness of the Referral Model if 65% of families accept referral for refraction/spectacles, which is the target in our hypothesis; with a power of 90%, an alpha-error of 0.05, and an intracluster correlation coefficient (ICC) (a measure of how similar children are to one another within schools: "clustering") of 0.20.

Randomization: An independent statistician having no contact with participants will generate the randomization sequence using a computer system that is inaccessible until after the school has agreed to join the trial. Schools will be stratified into two groups as Public and private. The schools in each stratified group will be randomly assigned to either the intervention (referral models) or control group (school model) in a 1:1:1 ratio with a block size of three to ensure balance. After randomization, the schools and the children in them will not be masked to their allocated intervention but staff assessing data for the main outcome will not know a child's group assignment.

Data to be acquired at baseline: Child: Age, gender, spectacles ownership, presenting and best corrected visual acuity in both eyes; refractive error in both eyes; distance of child's home from nearest Vision Center; brief spectacle attitude questionnaire; brief family Socio-Economic Status (SES) questionnaire[15]. Teacher: Brief questionnaire on attitudes and knowledge towards spectacles. Program: Survey of all program costs for screening and distribution for each model. Our cost-effectiveness analysis will be from the Program rather than the societal perspective, but the investigators will capture travel cost info from a 1% sample of randomly-selected children/families and capture information about teacher time spent in meeting with parents, sending notes to parents and encouraging children to wear spectacles in a 1 % random sample of Referral group teachers, in order to perform a sensitivity analysis of the impact of including these costs. Regarding programs costs, in the School model, where the optometrist team does the screening at school, the program

cost will be calculated by taking the cost of the primary and secondary screening, cost of the spectacles, and cost of delivering them. In the Referral model, the investigators will include the cost of primary screening, secondary screening at the vision centres and the cost of spectacles. In the Cost recovery model, the cost recovered by selling the spectacles (difference between retail price and cost of spectacles to the hospital) will be subtracted from the program cost. School: Urban versus rural, public versus private, size of the school, SES of community, and distance of the school from nearest Vision Center.

[figure not shown]
Follow-up schedule and follow-up data: Self-reported and observed spectacle wear to be ascertained at an un-announced follow-up at school 3 months after distribution of spectacles. Additionally, the following data for the Referral groups will be collected from the referral centre and verified from the children in a random sample of 10% of children: Did they visit the referral centre? Did they receive free spectacles? Did they elect to purchase upgrade spectacles? (in the Cost Recovery group). Children in the Referral groups not having received spectacles at the referral centres will receive them now, and so their visual acuity with spectacles and refractive power in each eye will be measured and recorded.

Data collection: An experienced project coordinator will be responsible for data collection and follow-up. The project coordinator will be thoroughly trained on the completion of the data collection forms.

Data Management Plan: The baseline data will be entered and stored in the database (“Reachsoft”), which is password protected. Other data for the study will be collected and entered by an external data entry operator and sent to the project manager to store it in a password-protected system. The collected data will be analyzed in de-identified fashion by the study statistician in India.

A copy of the final study data will be shared with Queen's University Belfast (QUB) under the data sharing and protection outlined in a Memorandum of Understanding. The final dataset will be stored in the QUB database under QUB custody. The study team will have access to the data for research and analyses purposes only. Data will be stored for 5 years after the end of the study.

- **Study Flow:**

Data Analytic Plan: Data will be analysed using STATA 15. The primary and secondary outcomes will be compared between the three randomized groups using an intention to treat approach with and without adjustment for the baseline child, school and teacher factors listed above. Our primary outcome is cost-effectiveness (cost per child identified needing spectacles, who gets and is still wearing them 3 months later). The investigators have two hypotheses about this primary outcome:

Primary hypothesis: The improved Referral model which involves teachers contacting families will sufficiently improve uptake that this Referral model will be more cost-effective than the School model.

Proposed analysis: Cost per child identified needing spectacles (program perspective, as above), who gets and is still wearing them 3 months later, compared between School and Referral model.

Secondary hypothesis: Cost recovery from the Referral + Cost Recovery Model will make this more cost-effective than either of the other models.

Proposed analysis: Cost per child identified needing spectacles, who gets and is still wearing them 3 months later, compared between the Referral + Cost Recovery and other groups.

The investigators will also do a stratified analysis comparing the main outcome between groups at each of the 3 participating hospitals. Additional stratified analyses / balancing of the main outcome between groups will be done for public versus private schools and rural versus urban schools.

The investigators will be using Latent class regression analysis and Finite mixture models to analyze the main outcome.

Monitoring: A dedicated Project Manager, [name], will be responsible for the overall planning, implementation, coordination, and monitoring and evaluation in the project. She will recruit a local project assistant at each site to coordinate all activities at the community level and at the base hospital and Vision Centers; ensure that appropriate planning is done for organizing and implementing screening activities; and coordinate availability of trained manpower, equipment, and facilities. [name] will interact with Orbis India Project Managers for the REACH program.

Research advisors [name], [name], and [name] each has decades of familiarity with refractive error research in children, and all have engaged in multiple research projects in India. Additionally, [name] has worked with Orbis since 2009 and is now its Director of Research.

Ethical considerations: Ethical approval has been received from two of the partners in India and Queen's University Belfast and will be sought from the additional partner. In the two Referral model groups, children who need to go to the facility to get spectacles but do not do so within the three-month period will receive free spectacles at closeout, so that no child requiring treatment will be left untreated.

Conditions

Conditions: Childhood Refractive Error

Keywords: Child, refractive error, myopia, school screening, cost effectiveness, India

Study Design: Cluster-randomised, investigator-masked trial

Study Type: Interventional

Primary Purpose: To determine the most cost-effective approach to school-based vision screening and spectacles delivery in India . Health Services Research

Study Phase: N/A

Interventional Study Model: Parallel Assignment

Randomization, Interventions: This is a cluster randomized trial, with eligible children allocated to the intervention that their school was randomized to receive. This will be one of the following three:

School Model (47 schools): Vision screening will be carried out by the vision screeners; refraction will be done at the schools by refractionists; and children who need them will be given free spectacles at the school within two weeks.

Referral Model (47 schools): Vision screening carried out by the vision screeners; and children are referred to nearby Vision Center/ secondary center for refraction and delivery of free spectacles. Teachers will contact families not presenting for follow-up care and for spectacle compliance through SMS, phone call and notations in the school diary.

Referral Model + Cost Recovery (47 schools): Vision screening carried out by the vision screeners; children referred to Vision Center for refraction and delivery of spectacles with an option to purchase "upgrade spectacles" (which was shown to be appealing to families in the recent PRICE study[14]. These spectacles have scratchproof coatings and designs selected to appeal to local children. Teachers will contact families not presenting for follow-up care through SMS, phone call and notations in school diary.

Number of Arms: 3

Masking: Single (Investigator) : Investigators assessing the components of the main study outcome will be masked to the study group assignment of the school.

Staff assessing data for the main outcome will be masked to a child's group assignment.

Allocation: Randomized

Enrollment: 141 schools [Anticipated]

Arms and Interventions

Experimental: School Model

Vision screening will be carried out by the vision screeners; refraction will be done at the schools by refractionists; and children who need them will be given free spectacles at the school within two weeks.

Experimental: Referral Model

Referral Model (47 schools): Vision screening carried out by the vision screeners; and children are referred to nearby Vision Center/ secondary center for refraction and delivery of free spectacles. Teachers will contact families not presenting for follow-up care and for spectacle compliance through SMS, phone call and notations in the school diary.

Experimental: Referral Model + Cost Recovery

Referral Model + Cost Recovery (47 schools): Vision screening carried out by the vision screeners; children referred to Vision Center for refraction and delivery of spectacles with an option to purchase "upgrade spectacles" (which was shown to be appealing to families in the recent PRICE study[14]. These spectacles have scratchproof coatings and designs selected to appeal to local children. Teachers will contact families not presenting for follow-up care and for spectacle compliance through SMS, phone call and notations in school diary.

Outcome Measures

Primary Outcome Measure:

Program cost-effectiveness

Program cost per child identified with correctable refractive error, who receives spectacles and wears them at an un-announced visit 3 month after distribution. Income from sales of spectacles in the "Referral + Cost Recovery" group will be subtracted from the program costs. The groups will be compared, with and without adjustment for baseline characteristics.

[Time Frame: 13 months]

Secondary Outcome Measures:

Proportion of children receiving spectacles who are wearing them at the time of un-announced 3-month follow-up

Purchase rates of upgrade spectacles in the Referral + Cost Recovery Group

Teacher and student reports of rates of teacher interventions in the two Referral groups (contact of parents to complete referral, encouraging children to wear spectacles)

Baseline visual acuity with spectacles

Refractive power of spectacles

[Time Frame: 12 months]

Eligibility

Minimum Age: 10 Years

Maximum Age: 15 Years

Sex: All

Gender Based: No

Accepts Healthy Volunteers: No

Criteria:

Inclusion Criteria:

Eligibility: Enrolment criteria:

- Children in randomly-selected 6th to 10th grades in selected schools with presenting visual acuity (that is, wearing spectacles if spectacles are owned at baseline) $\leq 6/9.6$ (0.2 LogMAR) in either eye.
- Children who already own spectacles will be requested to bring their spectacles on the day of screening, and children whose vision with existing spectacles meets study criteria will be eligible.
- Entry into the trial only requires that a child fail vision screening, which is assessed in the same way for all three randomized groups.

Exclusion Criteria:

- Parents returning the form indicating they do not wish their child to participate;
- no Vision Center within 50 km of the child's home (a rare occurrence in the REACH network).
- If the child is incapable of completing visual acuity screening in both eyes for any reason.

References

Citations:

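### The stated 90% power does not follow from the plan's own inputs: 47 schools per arm give about 39-54% on referral acceptance and, under stated assumptions, about 9-16% on cost per wearing child

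*Combined protocol and SAP*

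**What the plan says.** The Sample size paragraph (Experimental plan) assumes 3% prevalence of refractive error, at least 300 children per school, 95% receipt of spectacles in the School Model, 40% wear at three months in both models, and costs of US$1.30 (School) and US$0.80 (Referral) per child screened. It says the two models are equally cost-effective "if 58.5% of families accept referral to receive refraction and spectacles in the Referral Model". It then says that 141 schools, 47 per group, "would be sufficient to detect significantly better cost-effectiveness of the Referral Model if 65% of families accept referral for refraction/spectacles", "with a power of 90%, an alpha-error of 0.05, and an intracluster correlation coefficient (ICC") of 0.20.

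The paragraph gives no formula, test, sidedness or cost variance, and does not say which outcome the ICC describes. The Data Analytic Plan makes the primary comparison the cost per child needing spectacles "who gets and is still wearing them 3 months later, compared between School and Referral model". It later names "Latent class regression analysis and Finite mixture models to analyze the main outcome" without giving a model.

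**The concern.** The target (65%) is only 6.5 percentage points above the break-even (58.5%). At 3% prevalence each school contributes few children, and an ICC of 0.20 removes more than half of their information. Power of 90% from 47 schools per arm looked implausible even if only acceptance is uncertain. It looked more so for a cost per wearing child, where wear at 40% adds variance in both arms.

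The 90% is the justification for 141 schools. If true power is far lower, the trial can meet its own 65% target and still return a non-significant comparison. A reader relying on the stated power could then take that result as evidence that the Referral Model is not more cost-effective.

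**Working it through.** All inputs are from the Sample size paragraph unless marked as assumptions.

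**1. Break-even (reproduces).** Costs per wearing child are equal when acceptance is 0.95 × 0.80/1.30 = 0.5846, the plan's 58.5%. The cost model has therefore been read as intended.

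**2. Effective sample size per arm.**
- Children with refractive error per school: 300 × 0.03 = 9
- Per arm: 47 × 9 = 423
- Design effect: 1 + (9 − 1) × 0.20 = 2.6
- Effective n: 423/2.6 = 162.7

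**3. Acceptance against a fixed 58.5%.** This treats costs, School receipt and wear as known, so only Referral acceptance varies.
- SE = √(0.65 × 0.35/162.7) = 0.0374
- z = 0.065/0.0374 = 1.74
- Power = Φ(1.74 − 1.96) = 41% two-sided; Φ(1.74 − 1.645) = 54% one-sided
- Using the variance at 58.5% gives 39% and 52%.
- Beta-binomial simulation with school-level standard errors gives 40-42% and 52-54%.

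**4. Can larger schools rescue it?** As cluster size m grows, effective n = 47m/(1 + (m − 1) × 0.20) tends to 47/0.20 = 235. Power is then at most 55% two-sided or 67% one-sided.

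**5. The defined primary outcome.** Assumptions: log-ratio test, unit costs fixed, ICC 0.20 on wear in both arms.
- Wearing proportion: School 0.95 × 0.40 = 0.38; Referral 0.65 × 0.40 = 0.26
- Cost per wearer: School 1.30/(0.03 × 0.38) = US$114.0; Referral 0.80/(0.03 × 0.26) = US$102.6; ratio 0.90, log −0.106
- SE = √(0.62/(0.38 × 162.7) + 0.74/(0.26 × 162.7)) = 0.166
- z = 0.106/0.166 = 0.64
- Power: 9-10% two-sided, 16% one-sided (simulation 10-11% and 16%)
- Expected 95% CI: exp(−0.106 ± 1.96 × 0.166) = 0.65 to 1.25

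**6. Variants, 47 schools per arm.**

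| Test | Two-sided | One-sided |
|---|---|---|
| Acceptance v 58.5%, ICC 0.20, 9 per school | 39-41% | 52-54% |
| Same, 30 per school (assumes 1,000 children) | 48-50% | 60-62% |
| Same, unlimited school size | at most 55% | at most 67% |
| Acceptance v 58.5%, ICC 0, 9 per school | 77-80% | 86-88% |
| Cost ratio, wear held fixed, ICC 0.20 | 42% | 55% |
| Cost per wearer, ICC 0.20 | 9-10% | 16% |
| Cost per wearer, ICC 0.05 | 14% | 22% |
| Cost per wearer, ICC 0 | 18% | 27% |

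**7. What 90% power would take at ICC 0.20.** For step 3, effective n = (1.960 + 1.282)² × 0.65 × 0.35/0.065² ≈ 566 two-sided, so 566 × 2.6/9 ≈ 163 schools in the Referral arm alone. Across variance choices the range is 163-174 two-sided and 133-142 one-sided. For step 5 it is about 1,209 schools per arm two-sided or 986 one-sided. With 47 schools per arm, the acceptance detectable at 90% power is about 69-71% for step 3, and about 89% (one-sided) to 93% (two-sided) for step 5.

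**The case against.** The strongest reply concerns the ICC. The plan does not say which outcome 0.20 describes, 300 is a minimum, and under the inclusion criteria "Entry into the trial only requires that a child fail vision screening", so more than 9 children per school may be referred. If acceptance clusters much less than 0.20, the fixed-threshold test can approach 90%: ICC 0.05 with 30 referred per school gives 89-91% two-sided, and ICC 0 with 12 referred gives about 88-90%. The no-clustering row at 9 per school is therefore not an upper bound. This stands, but it replaces the plan's ICC with a much smaller one. At 0.20, the limit in step 4 holds however many children are referred.

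Second, the 9-16% rests on a model that the plan does not specify. The paragraph varies only acceptance, and holding wear fixed raises power on the cost ratio to 42% or 55%, with an expected 95% CI of about 0.80 to 1.01. The 9-16% is indeed one scenario. However, wear is part of the defined outcome, so fixing it omits real variance, and even that variant is far from 90%.

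Third, the adjusted analyses and the latent class and finite mixture models were not modelled, because they are not specified. Adjustment might add power, but the plan gives no figure for it.

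Counting more schools does not help either. Pooling both Referral arms at 9 per school gives 66-69% or 77-79%. A one-sided test reaches about 90% if all 141 schools count as one group, or if the 94 pooled schools count all 300 children each. Neither is the planned School v Referral comparison.

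**Conclusion.** The 90% is wrong as written. At the plan's 47 schools per arm, 9 children with refractive error per school and ICC 0.20, power is 39-41% two-sided or 52-54% one-sided on the most favourable simple reading, acceptance against a fixed break-even. No school size takes that above 55% or 67%. This conclusion needs only that 0.20 applies to acceptance.

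On cost per wearing child, power is about 9-10% or 16%. That figure also assumes a log-ratio test, fixed unit costs and ICC 0.20 on wear; between-school cost variation would probably lower it. Without any clustering it is 18% or 27%, with an expected 95% CI of 0.74 to 1.10. The exact value depends on choices the plan leaves open, but the shortfall from 90% at the stated ICC does not. The documents do not say how a non-significant result would be read; the risk of misreading is a consequence of the stated power. This must be corrected.

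**What to change.** Keep 141 schools and correct the claim made for them:

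1. Name the test for the primary School v Referral comparison and its sidedness, and say which outcome the ICC of 0.20 describes.
2. Base the calculation on about 9 children with refractive error per school, or on the expected number referred if acceptance is the tested quantity.
3. Replace the 90% with the power that 47 schools per arm deliver under that test, as a range with its assumptions, or with the acceptance detectable at 90% power.
4. Add to the Data Analytic Plan that a non-significant primary result will be interpreted from its confidence interval, not as evidence that the Referral Model is not more cost-effective. This is a safeguard that the low power makes worthwhile, not part of the arithmetic correction.

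The cost is a rewritten paragraph and one added sentence, with no extra schools. The downside is a much less favourable stated power.

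### Hospital is neither a randomisation stratum nor a listed covariate, so chance imbalance by hospital can add avoidable noise to the pooled School versus Referral comparison

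*Combined protocol and SAP*

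**What the plan says.** All references are to the combined protocol and SAP.

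- **Sample size:** "A total of 141 schools (47 in each of three groups) across three participating hospitals would be sufficient". The number of schools per hospital is not given.
- **Randomization:** "Schools will be stratified into two groups as Public and private". Allocation within each group is "in a 1:1:1 ratio with a block size of three to ensure balance". No separate lists per hospital are described, and the order in which schools enter is not stated.
- **Data Analytic Plan:** "The investigators will also do a stratified analysis comparing the main outcome between groups at each of the 3 participating hospitals". The main comparisons are made "with and without adjustment for the baseline child, school and teacher factors listed above".
- **Data to be acquired at baseline:** the school-level factors are "School: Urban versus rural, public versus private, size of the school, SES of community, and distance of the school from nearest Vision Center". Hospital is not among them, nor is it among the child or teacher factors. On costs, the Referral model counts "the cost of primary screening, secondary screening at the vision centres and the cost of spectacles", and the Cost Recovery margin is the "difference between retail price and cost of spectacles to the hospital".

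**The concern.** The plan treats hospital as an analysis stratum but not as a randomisation stratum, and does not list it for adjustment. The by-hospital analysis suggests that the investigators think hospital may matter. It is a reasonable inference that it does: part of the programme cost arises at the facilities, and referral uptake, which the Background calls the most important determinant of cost-effectiveness, may depend on local services.

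If cost per successful child differs between hospitals, an arm that happens to draw more schools from a dearer hospital looks worse for that reason alone. Neither the allocation scheme nor the listed covariates remove this from the pooled School versus Referral contrast. What is at stake is precision, set against a small planned effect.

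**Working it through.** **Inputs from the documents.** 141 schools, 47 per arm, three hospitals, 1:1:1 in blocks of three within public and private. School model: US$1.30 per child screened, 95% receiving spectacles. Referral model: US$0.80 and a target uptake of 65%. Spectacle wear of 40% in both models cancels in the ratio.

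**Assumptions, because the documents are silent.** 47 schools per hospital, half of them private. Entry order is varied.

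**1. The planned effect.**
- The plan's break-even uptake reproduces: 0.95 × 0.80/1.30 = 0.585, the stated 58.5%.
- The planned cost-effectiveness ratio, Referral over School, is (0.80/0.65)/(1.30/0.95) = 1.231/1.368 = 0.90, an advantage of about 10%.

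**2. Arm imbalance within hospitals.** The expected arm size within a hospital is 47/3, about 16 schools. Results come from 20,000 simulated allocations per row. The gap is the largest difference between any two arms in any of the three hospitals.

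| Strata | Entry order | Median gap | 95th percentile | P(gap ≥ 5) | P(gap ≥ 8) |
|---|---|---|---|---|---|
| Sector only (as planned) | fully mixed | 7 | 12 | about 85% | 46% |
| Sector only | two hospitals mixed, third follows | 5 | 10 | 55% | 17% |
| Sector only | one hospital at a time | 2 | 3 | 0 | 0 |
| Hospital × sector, blocks of 3 | fully mixed | 1 | 2 | 0 | 0 |

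With unequal hospitals (71/42/28 assumed) and mixed entry, the median is still 7 under the planned scheme, and 2 with hospital × sector strata.

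The bound of 2 in the last row comes from incomplete final blocks. Each hospital has two strata, and a broken block of three adds at most one school to a gap. Complete blocks would give 0.

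**3. The primary pair of arms.** Under mixed entry the allocation is close to simple sampling without replacement. The variance of (School minus Referral) in one hospital is then 47 × (94/140) × (2/9 + 2/9 + 2/9) = 21.0, so the SD is 4.6 schools. A normal approximation gives P(difference ≥ 5) = P(|Z| > 4.5/4.6), about 33%, and P(≥ 8) = P(|Z| > 7.5/4.6), about 10%. Simulation agrees, with a median difference of 3.

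**4. Effect on the pooled contrast (illustration).** Suppose that cost per successful child differs by −20%, 0 and +20% across hospitals. No document supports this or any other spread.
- The variance between schools due to hospital is (141/140) × (0.04 + 0 + 0.04)/3 = 0.0269.
- The SD of the chance shift between two arms of 47 is √(0.0269 × 2/47) = 0.034, or 3.4%.
- Simulation of the blocked scheme with mixed entry gives SD 3.4% and a 95th percentile of 6.7%. With hospital as a stratum it gives 0.6% and 0.9%.
- A spread of ±10% halves all of these. With no spread they are zero.

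**5. Effect on within-hospital comparisons.** The variance is proportional to 1/n₁ + 1/n₂.
- 12 v 20 schools against 16 v 16: (1/12 + 1/20)/(2/16) = 1.067, about 7% more.
- 13 v 18 against 15.5 v 15.5: (1/13 + 1/18)/(2/15.5) = 1.027, about 3% more.

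**The case against.** **Hospital-level cost is an inference.** A reader might infer that the documents show costs to belong to each hospital. They do not. Programme costs are to be surveyed by model, and the sample size uses a single cost per model. The one phrase naming the hospital's own cost concerns the Cost Recovery margin, which is outside the primary contrast. This stands, and so the shift in step 4 is only an illustration. Distance to the nearest Vision Center is already a listed covariate and covers part of access, but it is not a substitute for hospital.

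**Entry order may already give balance.** Under Ethical considerations, approval is in place at two Indian partners and still to be sought at the third, so staggered entry is plausible. Entry one hospital at a time would largely remove the problem under the planned scheme. This also stands, but the documents do not promise that order.

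**This is not bias.** A reader might infer a biased trial or spoiled within-hospital comparisons. Neither follows. Chance imbalance leaves the randomised comparison valid, and comparing arms inside a hospital removes hospital differences from the contrast. Only the few percent of precision in step 5 is lost.

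**More strata have a price.** Schools are unmasked and blocks are fixed at three. With one list per hospital and sector, local staff who know earlier allocations could work out the last one in a block. Pooling hospitals partly hides the position in the block. This is a real cost, and the fix has to deal with it.

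**Conclusion.** The gap is real and worth closing. Hospital is used to split the main outcome but is protected by neither the allocation scheme nor the listed adjustment.

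The consequence is avoidable noise in the pooled School versus Referral comparison, whose planned advantage is about 10%. The median largest arm gap is 2 to 7 schools, depending on an entry order that the plan does not state. The figure of about 85% for a gap of 5 or more belongs to fully mixed entry and to the worst of three hospitals and all arm pairs, so it should not be read as the expected state of the trial. How far any gap moves the result depends on between-hospital variation, which the documents do not give.

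**What to change.** 1. **Analysis.** Include hospital and public/private as factors in the primary analysis model, and state that this adjusted analysis is the primary one. Public/private is already listed, so hospital is the only addition. It costs nothing and is possible even if allocation has begun.
2. **Randomisation, if allocation has not started.** Stratify by hospital and public/private: six strata, on average 141/6 = 23.5 schools or about eight blocks of three each. This needs a change to the list generator only.
3. **Limit the downsides.** There can be up to six incomplete final blocks, and separate lists with fixed blocks of three are easier to predict. Either vary the block size (3 and 6) or allocate each stratum's schools as a batch once they have agreed to join. Varied blocks relax the balance slightly: a broken block of six can add 2 to a gap, so the bound per hospital rises from 2 to 4 (simulated median 2, 95th percentile 3).
4. **Reporting.** State the number of schools per hospital and the order in which hospitals enter.
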